1.2 Introduction to investigational treatment(s) and other study treatment(s)

1.2.1 Overview of deferasirox

Deferasirox (company research code: ICL670; trade name: Exjade[®], JadenuTM) is an orally active iron chelator that binds iron with high affinity and promotes excretion of excess iron, primarily in the feces.

1.2.1.1 Non-clinical experience

In vitro and *in vivo* studies demonstrated the high potency of deferasirox in mobilizing tissue iron and promoting iron excretion, and deferasirox was eliminated from the body by hepatic glucuronidation and biliary excretion. Preclinical studies demonstrated that deferasirox did not affect fertility and is neither teratogenic nor carcinogenic. Based on non-clinical studies, use in humans includes restricted in pregnancy and breast feeding and requires renal function monitoring and periodic ocular testing. Detailed preclinical information on deferasirox is in the current Investigators' Brochure.

1.2.1.2 Clinical experience

Deferasirox was approved for the treatment of chronic iron overload due to frequent blood transfusions (aged 2 years and older in more than 100 countries) and non-transfusion-dependent thalassemia (aged 10 years and older in more than 70 countries). It is available as dispersible tablets (DT, trade name: Exjade[®]) and film-coated tablets [(FCT), tradename: JadenuTM in the US (United States), Canada, and some other countries; and as Exjade in EU (European Union))].

Since approval on 2 November 2005, the dose-dependent efficacy of chelation therapy has been demonstrated for deferasirox DT in several large clinical trials with over 8121 patients exposed for up to 5 years and

The safety profile of

deferasirox has been well characterized with the dispersible tablet formulation.

Because of the chronic nature of chelation therapy and the importance of patient compliance, an improved deferasirox formulation for oral administration was developed. FCT contains the same active substance, but was strength-adjusted to achieve comparable exposure to the dispersible tablet. It is available in three dose strengths (90 mg, 180 mg and 360 mg) and is dosed based on weight. It can be taken with or without a light meal (See Appendix 14.2 for examples). The currently available clinical trial data with the FCT formulation suggests a safety and efficacy profile that is consistent with the known profile of the DT deferasirox formulation.

2 Rationale

2.1 Study rationale and purpose

Iron overload due to HH typically manifests between the third and sixth decades of life and is more common in males. If untreated, iron accumulates in the organs and causes tissue injury and dysfunction. Therefore, these patients might benefit from an iron chelator. If untreated in the liver, iron deposition will cause fibrosis, which may ultimately progress to cirrhosis and increased susceptibility to hepatocellular carcinoma. (Bacon 2011, Beaton and Adams 2007). Effects on the liver are exacerbated in alcoholics and in patients with chronic hepatitis B or C. Other manifestations include arthropathy, endocrinopathies (hypogonadism, sexual dysfunction, pancreatitis, or diabetes), and rarely, cardiomyopathy/cardiac failure with mortality (Niederau 1996, Morrison 2003).

Although phlebotomy is generally tolerated well and is very effective, it may not always be feasible due to inconvenient clinic visits and discomfort associated with the procedure; therefore, compliance may wane with time. A small percentage of patients may be ineligible for phlebotomy due to reduced venous access, congestive heart failure, or anemia. Oral iron chelation therapy will provide another option for patients either unwilling or unable to undergo a regular phlebotomy regimen.

The aim of this study is to evaluate the efficacy and safety of deferasirox FCT versus phlebotomy for the management of iron overload in adults with HH at risk of iron-related morbidity. This evaluation will provide information on the two treatment options in terms of the response rate of proportion of patients reaching the study target SF $\leq 100 \ \mu g/L$ and their associated safety profiles.

Ocular disturbances have been reported with deferasirox. Although no additional ocular risk have emerged over 10 years of Exjade on the market and from clinical trials, the FDA requires further confirmation on ocular safety with a controlled study in chelation-naive patients. Therefore, in addition to exploring the safety and efficacy of deferasirox FCT in HH, this study is being conducted to fulfill an FDA post-marketing requirement [PMC 750-10 (Exjade) /PMR 2888-8 (Jadenu)] to provide additional randomized data to confirm the ocular safety profile of deferasirox through detailed ophthalmologic assessments in patients treated with deferasirox FCT for 2 years.

2.2 Rationale for the study design

This will be an open-label design since phlebotomy cannot be blinded. The safety and response rate of deferasirox versus the standard of care phlebotomy in reducing iron in adult patients with HH will be evaluated.

Patients will be randomized 2:1 to deferasirox FCT or phlebotomy.

2.3 Rationale for dose and regimen selection

A Phase I/II dose escalation study in HH (CICL670A2202), deferasirox DT 10 to 15 mg/kg/day had an acceptable safety profile (Phatak 2010). In a one-year Phase 2 study in HH patients (CICL670EBR14T), deferasirox DT 10 ± 5 mg/kg/day was well tolerated and effective in reducing iron burden (Cancado 2015). Based on these 2 studies, the starting dose in this trial will be deferasirox FCT 7 mg/kg/day (equivalent to deferasirox DT 10 mg/kg/day). A dose adjustment between the two formulations is required because bioavailability was increased in FCT, and an equivalent deferasirox AUC was achieved at a lower dose, e.g., 1080 mg FCT vs. 1500 mg DT (CICL670F2102 study).

2.4 Rationale for choice of combination drugs

Not applicable

2.5 Rationale for choice of comparators drugs

The control arm is phlebotomy which is the standard of care for removing excess iron in nonanemic patients with HH. Most have unimpaired erythropoiesis so as blood is extracted, bone marrow is stimulated to make new red cells. Iron stores are reduced when iron is transported to make hemoglobin. Depending on the hematocrit, each unit of blood (typically 500 mL) contains 200-250 mg iron and removal by phlebotomy decreases the ferritin level by approximately 30 μ g/L (Bacon 1997). When SF is above normal, consensus opinion is that there is a benefit in early iron removal on a weekly or biweekly basis until iron stores are in the normal range (SF = 50-100 μ g/L), then thereafter, every two to four months to prevent re-accumulation of iron absorbed from a regular diet (EASL 2010, Tavill 2001). Although there are no evidence-based studies, SF is the accepted standard for initiating and monitoring response to achieve a SF \leq 100 μ g/L, which is used as the primary endpoint of this study. Phlebotomy will be conducted at a frequency determined by the investigator's clinical practice.

2.6 Risks and benefits

Appropriate eligibility criteria and specific dose modification and stopping rules are included in this protocol. Risk is minimized by compliance with the eligibility criteria and study procedures, close clinical monitoring, and protocol-defined dose modification rules. The available clinical trial data with FCT suggests a safety and efficacy profile consistent with the known profile of the DT formulation. As with any treatment or procedure, deferasirox FCT or phlebotomy may cause unforeseen risks, which could be serious.

The efficacy and safety of deferasirox have been evaluated in a large prospective clinical trials program that has generated long-term data in iron overload patients with transfusional iron overload (thalassemia major, sickle cell disease, and myelodysplasia syndrome) (Cappellini 2006, Vichinsky 2007) and with non-transfusion dependent thalassemia. The accumulated data provides an acceptable safety and tolerability profile across all age groups. The majority of adverse events (AEs) are mild to moderate and manageable with dose adjustments or interruptions. The available clinical trial data with FCT suggests a safety and efficacy profile consistent with the known profile of the DT formulation.

No new safety concerns regarding ocular toxicity have emerged since the approval of deferasirox. The most common visual acuity events were blurred vision and visual impairment. The most common lens opacity was cataract, and retinal changes were due to degeneration, retinopathy, maculopathy or optic neuritis. As stated in the current Exjade and Jadenu USPIs, ocular disturbances (lens opacities, cataracts, elevations in intraocular pressure, and retinal disorders) were reported at a frequency of <1% with deferasirox therapy in the clinical studies. Optic neuritis occurs in 0.01% to 0.1% of patients. Ocular safety is a key secondary endpoint in this study, and ocular assessments are required to gather safety information.

Assess the first time to response (defined as SF \leq 100 μ g/L) between the deferasirox and phlebotomy treatment groups.	Time to reach target SF \leq 100 µg/L in the deferasirox and phlebotomy arms for the first time.	

4 Study design

4.1 Description of study design

This is a Phase II, multicenter, open-label, randomized two-year study in 150 adults confirmed by HH genotype with iron overload. Eligible patients will be identified during a 4-week screening period, then randomized in a 2:1 ratio (100 patients to deferasirox FCT and 50 patients to phlebotomy), and treated for 24 months (104 weeks). After end of treatment (EOT), there is a standard 30-day safety follow-up. Please refer to Section 7 for screening and assessment details.

An initial dose of deferasirox FCT 7 mg/kg/day will be used for 3 months (12 weeks), then adjusted according to the ferritin level. Dose adjustments based on safety are allowed at any time.

Phlebotomy will be conducted at a frequency determined by the physician.

Both phlebotomy and deferasirox FCT must be interrupted when the study-defined target SF $\leq 100 \ \mu g/L$ is achieved. Deferasirox FCT may be reinitiated when SF $\geq 300 \ \mu g/L$, according to deferasirox label; phlebotomy may be reinitiated when SF $> 100 \ \mu g/L$, based on standard of care practice. Following end of treatment, patients will enter a 30-day safety follow-up period. Concomitant medications and AEs will be collected during this period.

4.1.1 Post-treatment Ocular Follow-up

If a patient discontinues from treatment in either arm and has completed at least 6 months of assessments, they will be encouraged to continue in a Post-treatment Ocular Follow-up phase to undergo scheduled ocular exams every 6 months to receive at least 5 ophthalmological examinations. If a patient discontinues between the scheduled 6-month exams, an ophthalmologic exam is part of the EOT and they will continue their regular schedule of ophthalmological exams every 6 months for a total of 6 ocular examinations. Please refer to

Section 7.2.2.5 for details. One month prior to each ophthalmological visit, a site coordinator will call to confirm the upcoming visit.

4.2 Timing of interim analyses and design adaptations

Not applicable

4.3 Definition of end of study

The end of study (EOS) will be when the latest of the following will have occurred:

- A) All patients completed 24 months of treatment, and patients completed their EOT visits and 30-day safety follow-up; OR
- B) Patients who discontinued from treatment prior to 6 months, or after 6 months but did not agree to participate in Post-treatment ocular follow-up: patients completed their EOT visits and 30-day safety follow-up; OR
- C) Patients who discontinued from treatment after 6 months and agreed to Post-treatment ocular follow-up: patients completed their EOT visits, 30-day safety follow-up, and Post-treatment ocular follow-up up to Month 24.

After completing the study or discontinuing from study treatment, patients will receive standard of care. The primary analysis will be based on the final locked data and will be summarized in the clinical study report (CSR).

4.4 Early study termination

The study can be terminated at any time for any reason by Novartis. If this occurs, the patient should be seen as soon as possible and the same assessments should be performed as described in Section 7.1.5 for a discontinued or withdrawn patient. The investigator may be informed of additional procedures to be followed in order to ensure that adequate consideration is given to the protection of the patient's interests. The investigator will be responsible for informing IRBs and/or ECs of the early termination of the trial.

5 Population

5.1 Patient population

One hundred and fifty adult HH patients with homozygous C282Y genotype and iron overload (based on elevated transferrin saturation and SF) may enroll if they meet all inclusion and none of the exclusion criteria.

5.2 Inclusion criteria

Written informed consent must be obtained prior to any screening procedures.

Patients eligible for inclusion must meet **all** following criteria prior to receiving study treatment:

- 1. Male or female \geq 18-years-old
- 2. Documented genotype testing confirming homozygous for the C282Y mutation (C282Y/C282Y)
- 3. Transferrin saturation \geq 45% (at either screening visit)
- 4. Serum ferritin (SF) \geq 500 µg/L (at either screening visit)

5.3 Exclusion criteria

- 1. Medical conditions that preclude inclusion:
 - Iron overload not due to HH
 - Condition which might significantly alter the absorption, distribution, metabolism or excretion of oral deferasirox
 - Systemic disease which prevents taking study treatment or any contraindication to phlebotomy
 - Inflammatory condition or immunological disease which may interfere with the SF interpretation, such as an active infection, collagen vascular disorders, irritable bowel syndrome, lupus, or immune thrombocytopenia
 - Significantly impaired gastrointestinal function or disease that may significantly alter the absorption of oral deferasirox, e.g. ulcerative diseases, uncontrolled nausea, vomiting, diarrhea, malabsorption syndrome, or small bowel resection.
 - Psychiatric or addictive disorder which prevent giving informed consent or undergoing any of the treatment options or unwilling or unable to comply with the protocol
 - Uncontrolled or significant cardiac disease or symptomatic cardiac arrhythmias, e.g., sustained ventricular tachycardia and clinically significant second or third degree AV block without a pacemaker.
- Illicit drug use and/or alcohol use, defined as an average alcohol consumption greater than one standard drink a day for women or two standard drinks a day for men within the 12 months prior to enrolment. A standard drink is generally considered to be 12 ounces (or 355 ml) of beer, 5 ounces (or 148 ml) of wine, or 1.5 ounces (or 44 ml) of 80-proof distilled spirits
 - Cirrhosis, including Child-Pugh class A, B, and C, diagnosed by liver biopsy, elastography, radiologic exams, or clinical criteria
 - Active hepatitis B or C (hepatitis B carrier will be allowed)
 - History of HIV seropositivity (ELISA or Western blot)
 - Organ transplant recipient

- Malignancy of any organ system, treated or untreated, within the past 5 years whether or not there is evidence of local recurrence or metastases, except localized basal cell carcinoma of the skin, Hepatocellular carcinoma at any time is excluded.
- 2. Concomitant therapy that precludes enrollment:
 - Prior iron chelation therapy
 - Prohibited concomitant medications with deferasirox (see Section 6.4.3 for details)
- 3. Abnormal laboratory values:
 - Significant anemia that contraindicates phlebotomy (males with hemoglobin < 130g/L, females with hemoglobin < 120g/L) in both screening visit samples
 - Platelets $\leq 50 \times 10^9$ /L in both screening visit samples
 - Urine protein/urine creatinine ratio > 1.0 mg/mg in both non-first void urine screening visit samples
 - Creatinine clearance ≤ 40 ml/min, or use the locally approved contraindication limit in prescribing information if it is stricter, in both screening visit samples
 - Serum creatinine > 1.5 x ULN in both screening visit samples
 - ALT \geq 5 x ULN in both screening visit samples
 - Total bilirubin > 1.5 x ULN in both screening visit samples
- 4. Participation in an investigational study:
 - Observational registry study is allowable
 - Within 30 days prior to enrollment or within 5-half-lives of an investigational product, whichever is longer
- 5. Pregnancy and contraception:
 - Pregnant or nursing (lactating) women

Women of child-bearing potential, defined as all women physiologically capable of becoming pregnant, unless using appropriate methods of contraception Deferasirox may reduce the efficacy of hormonal contraception, thus it is recommended to use alternative methods of contraception such as

• Total abstinence

Periodic abstinence (calendar, ovulation, symptothermal, post-ovulation methods) and withdrawal are unacceptable methods.

- Female sterilization (bilateral oophorectomy with or without hysterectomy), total hysterectomy, or tubal ligation at least six weeks before taking study treatment. If oophorectomy alone, hormone levels must confirm menopause.
- Male sterilization (at least 6 months prior to screening). The vasectomized male must be the sole partner.
- Barrier methods of contraception: condom or occlusive cap For UK: spermicidal foam/gel/film/cream/vaginal suppository

- Placement of an intrauterine device or intrauterine system
- Women considered as post-menopausal and not of childbearing potential are allowed to be enrolled in the trial if they have had 12 months of natural (spontaneous) amenorrhea with an expected clinical profile, e.g., age appropriate and history of vasomotor symptoms.

See Section 8.4 for pregnancy reporting and follow-up requirements.

6 Treatment

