	arrhythmias, e.g., sustained ventricular tachycardia and clinically significant second or third degree AV block without a pacemaker.
	 Illicit drug use and/or alcohol use, defined as an average alcohol consumption greater than one standard drink a day for women or two standard drinks a day for men within the 12 months prior to enrolment. A standard drink is generally considered to be 12 ounces (or 355 ml) of beer, 5 ounces (or 148 ml) of wine, or 1.5 ounces (or 44 ml) of 80-proof distilled spirits
	• Cirrhosis, including Child-Pugh class A, B, and C, diagnosed by liver biopsy, elastography, radiologic exams, or clinical criteria.
	 Active hepatitis B or C (hepatitis B carrier will be allowed)
	 History of HIV seropositivity (ELISA or Western blot)
	 Malignancy of any organ system, treated or untreated, within the past 5 years whether or not there is evidence of local recurrence or metastases, except localized basal cell carcinoma of the skin. Hepatocellular carcinoma at any time is excluded.
	2. Prior iron chelation therapy, prohibited concomitant medications with deferasirox.
	3. Abnormal laboratory values:
	 Significant anemia that contraindicates phlebotomy (males with hemoglobin <130g/L, females with hemoglobin <120g/L in both screening visit samples
	 Platelets ≤ 50 x 10⁹/L in both screening visit samples
	 Urine protein/urine creatinine ratio > 1.0 mg/mg in both non-first void urine screening visit samples
	• Creatinine clearance ≤ 40 ml/min in both screening visit samples
	 Serum creatinine > 1.5 x ULN in both screening visit samples
	 ALT ≥ 5 x ULN in both screening visit samples
	 Total bilirubin > 1.5 x ULN in both screening visit samples
	4. Participation in an investigational study:
	 Observational registry study is allowable
	 Within 30 days prior to enrollment or within 5-half-lives of an investigational product, whichever is longer
	5. Pregnancy and contraception:
	 Pregnant or nursing (lactating) women
	 Women of child-bearing potential unless using appropriate methods of contraception
	 Post-menopausal and not of childbearing potential if she has had 12 months of natural (spontaneous) amenorrhea with an expected clinical profile.
Investigational and	Investigational drug: ICL670 (deferasirox):
reference therapy	Drug formulation: film-coated tablet (FCT)
	Control arm: phlebotomy
Efficacy assessments	 Primary efficacy endpoint will be assessed by response rate where response is defined by achieving target SF ≤ 100 µg/L on or before 24

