6.3 Dose modifications

6.3.1 Dose modification and dose delay

For patients who do not tolerate the protocol-specified dosing schedule, dose interruptions and/or reductions are either recommended or mandated in order to allow patients to continue the study treatment of defension FCT.

These dose modifications are summarized in Table 6-2. Deviations from the mandatory dose interruptions and/or reductions are not allowed. Permanent treatment discontinuation of deferasirox FCT is mandatory for specific events indicated in Table 6-2 or listed in Section 7.1.5.

These dose changes must be recorded on the Dosage Administration Record eCRF. It is important to keep an accurate dose adjustment records to enable an adequate evaluation of exposure.

Phlebotomy will be conducted at a frequency determined by the treating physician's clinical judgement for optimal iron control. The name of the facility, the date of phlebotomy, hematocrit level prior to phlebotomy and amount of blood withdrawn must be captured in Phlebotomy Record and local lab eCRFs. Phlebotomy must be interrupted when SF $\leq 100 \mu g/L$ and may be resumed when SF $\geq 100 \mu g/L$.

Novartis Amended Protocol Version 01 (Clean)

Table 6-2 Criteria for dose reduction / interruption and re-initiation of deferasirox FCT

Dose modifications for ICL670F2203		
Serum Ferritin (SF)		
After an initial starting dose (7 mg/kg/day) for 3 months (12 weeks), dose may be adjusted based on SF level. Dose increase cannot be more than 3.5 mg/kg/day at each adjustment.		
<300 µg/L	Decrease to 3.5 mg/kg/day	
300-1000 μg/L	Maintain 7 mg/kg/day	
>1000-2000 µg/L	Increase to 10.5 mg/kg/day	
>2000 µg/L	Increase to 14 mg/kg/day (higher doses are not allowed.)	
SF ≤ 100 μg/L at any time	Interrupt deferasirox FCT	
SF \geq 300 µg/L after dose interruption	Re-initiate deferasirox FCT 3.5 mg/kg/day. If SF continues to increase, increase to 7 mg/kg/day (maximum dose for maintenance phase).	
Body Weight		
Increase/decrease if weight changes >10% compared to baseline weight or weight at last dose adjustment due to a change in weight	Dose of study medication will be adapted using Dosing Table (provided in Appendix 14.1) When weight changes >10% compared to baseline weight or weight at last dose adjustment due to a change in weight, re-calculate dose. Smaller variations in weight (<10%) do not require dose adjustments.	
Investigations (Renal)		
Serum creatinine		
Single increase	Maintain dose and repeat assessment at next visit.	

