Increased creatinine ≥ 33% from baseline (average of 2 samples) resulting in creatinine > ULN x 2 consecutive samples (at least 2 weeks apart)	Decrease by 7 mg/kg/day or interrupt if already at 7 mg/kg/day or lower.	
If dose is decreased, but increasing creatinine > ULN	Interrupt treatment.	
After interruption, if creatinine returns to within normal limits on 2 consecutive visits.	Resume 50% of the most recent dose prior to interruption. If after another 4 weeks, creatinine remains stable, resume 100% dose (adjust for weight if needed).	
Creatinine clearance > 40 and < 60 mL/min	Caution in patients if there are additional risk factors that may impair renal function, such as concomitant medications, dehydration, or severe infection.	

Dece medifications for ICL 67052202	
Creatinine clearance < 40 mL/min	Deferasirox must be discontinued.
or increased serum creatinine > 2x age-appropriate ULN	
Urine protein/creatinine ratio	
Any proteinuria	If new or worsening pre-existing proteinuria (assessed by dipstick), collect a urine sample for assessment by the central/local laboratory.
	In case of a single increase of the urinary protein/creatinine ratio, repeat the assessment at the next visit.
> 0.5 urine protein/ creatinine ratio (mg/mg) in two consecutive non-first void urine samples (a minimum of 48h apart), if all other causes of proteinuria have been	Decrease deferasirox by 50%. If UPCR resolves (< 0.5mg/mg) at the next study visit, resume 100% dose.
excluded.	
> 1.0 (mg/mg) in two consecutive non-first void urine	Interrupt deferasirox FCT.
samples (a minimum of 48h apart)	If the increased UPCR resolves (< 0.5 mg/mg) at the next study visit, resume dose at 50% of the last dose. If UPCR remains within normal limits after 4 weeks at the 50% reduced dose, resume study medication at 100% of the last dose.
Persistent proteinuria	If proteinuria persists, discontinue study treatment if the investigator believes it is in the best interest of the patient.
	Novartis may be contacted by the investigator to discuss dosing options.
	Dose adjustment must be based on central/local laboratory results.
Investigations (Hepatic)	
Isolated direct (conjugated) Bilirubin elevation	
> ULN – 1.5 x ULN	Maintain dose
> 1.5 - 3.0 x ULN	Interrupt dosing. Monitor LFTs ^a weekly or more frequently if clinically indicated until resolved to \leq 1.5 x ULN: If resolved \leq 14 days, then maintain dose.
	If resolved > 14 days, then \downarrow 1 dose level (3.5 mg/kg/day FCT)

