7.1.2 Screening

Prior to screening, the patient must give full informed consent on the appropriate form. Once signed and dated by the patient, the investigator must review the study's inclusion and exclusion criteria with the patient to ensure that the patient is eligible to participate.

Two Screening Visits (at -4 weeks and at -2 weeks) are needed to perform key safety parameters prior to first dose administration per the deferasirox drug label and to confirm eligibility criteria.

Molecular testing of HH must be performed at the first screening visit if historical diagnosis is not available.

Specific safety assessments including ophthalmic and audiometry examinations, ECG, and cirrhosis assessment (unless diagnosis is available during the past 12 months, or SF is <1000 μ g/L and AST/ALT are normal) must be performed prior to starting study drug. It is preferred that they are performed at the first screening visit (-4 weeks), but to make it possible for the site to plan the examinations properly, these assessments can be performed at the second screening visit (-2 weeks).

SF, serum creatinine and urine protein/creatinine ratio will be measured at both screening visits and used to assess eligibility. SF should be obtained in the absence of any infection or inflammation.

Serum Pregnancy test will be required for females of child-bearing potential only.

The full list of assessments to be performed during screening is detailed in Table 7-1.

Re-screening is permissible on a case-by-case basis. All assessments at screening visits must be repeated if a patient is re-screened, except for molecular testing of HH, Ocular, Audiometry, ECG, and cirrhosis assessments. Please contact Novartis for guidance and see Section 7.1.2.2 on how to process screen failures.

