7.1.5 Discontinuation of study treatment

Patients may voluntarily discontinue from the study treatment for any reason at any time. If a patient decides to discontinue from the study treatment, the investigator must make a reasonable effort (e.g. telephone, e-mail, letter) to understand the primary reason for this decision and record this information in the patient's chart and on the appropriate eCRF pages. They may be considered withdrawn if they state an intention to withdraw, fail to return for visits, or become lost to follow-up for any other reason.

The investigator may discontinue study treatment for a given patient if; he/she believes that continuation would be detrimental to the patient's well-being.

Study treatment must also be discontinued under the following circumstances:

Pregnancy AEs listed in Table 6-2 Laboratory abnormalities listed in Table 6-2 Unwillingness to comply with the prescribed study treatment

Use of prohibited treatment refer to Section 6.4.3

Any other protocol deviation that results in a significant risk to the patient's safety

Patients who discontinue study treatment should NOT be considered withdrawn from the study. They should return for the assessments indicated in Section 7.2.2.5. If they fail to return for these assessments for unknown reasons, every effort (e.g. telephone, email, letter) should be made to contact them as specified in Section 7.1.8.

The investigator must also contact the IRT to register the patient's discontinuation from study treatment.

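### A low creatinine clearance at the last screening visit does not have to be repeated before randomisation and the first dose of deferasirox

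*Protocol*

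**What the plan says.** Protocol section 5.3 lists, among the abnormal laboratory values that exclude a patient, "Creatinine clearance ≤ 40 ml/min, or use the locally approved contraindication limit in prescribing information if it is stricter, in both screening visit samples". The protocol summary gives the same rule without the local limit: "Creatinine clearance ≤ 40 ml/min in both screening visit samples". Section 7.1.2 sets the schedule: "Two Screening Visits (at -4 weeks and at -2 weeks) are needed". Patients who meet all criteria are then randomised through the IRT, which holds the eligibility check (sections 6.5.2 and 7.1.2.1).

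For patients on deferasirox, the renal part of Table 6-2 has a row for "Creatinine clearance < 40 mL/min" with the action "Deferasirox must be discontinued". Section 6.3.1 gives the table its force: "Permanent treatment discontinuation of deferasirox FCT is mandatory for specific events indicated in Table 6-2 or listed in Section 7.1.5". Section 7.1.5 repeats this by listing, among the reasons for stopping, "Laboratory abnormalities listed in Table 6-2". The clearance row asks for no confirming sample. The row for a single rise in serum creatinine does: "Maintain dose and repeat assessment at next visit".

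**The concern.** Section 2.6 relies on the eligibility criteria and the dose-modification rules together to limit risk. For creatinine clearance the two meet at the same threshold but treat a single low value differently. During treatment, one value below 40 mL/min ends deferasirox. At entry, one such value, even the latest one, does not delay the first dose.

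A site can follow section 5.3 exactly and start a renally monitored drug in a patient whose latest known clearance is below 40 mL/min. If the Week 2 value is also below 40, that patient must stop. Patients are not replaced (section 7.1.5.1). The patient stays in the Full Analysis Set (section 10.1.1) and counts as a non-responder unless the ferritin target was already met (section 10.4.3).

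**Working it through.** **1. The entry rule applied to all four patterns** (limit 40 mL/min; illustrative values)

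| Week -4 | Week -2 | Both ≤ 40? | Result | Latest value < 40? |
|---|---|---|---|---|
| 44 | 44 | no | eligible | no |
| 38 | 44 | no | eligible | no |
| 44 | 38 | no | eligible | **yes** |
| 38 | 38 | yes | excluded | yes |

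Only the third row is at issue. In the second row the later sample has already cleared the low one.

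**2. Does another rule close the third row?**

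- *Stricter local limit.* It carries the same two-sample condition, so it moves the threshold but leaves the pattern open.
- *Serum creatinine > 1.5 × ULN.* This also needs both samples. The SAP formula (section 5.2.1) gives SCr = (140 − age) × weight × (0.85 if female) / (0.815 × CrCl). At CrCl 38, a woman of 75 years and 60 kg has 65 × 60 × 0.85 / 30.97 = 107 µmol/L, and a man of 80 years and 65 kg has 60 × 65 / 30.97 = 126 µmol/L. With an assumed ULN of 90 to 110 µmol/L (not in the documents), the limit is 135 to 165, so neither is excluded. A man of 70 years and 80 kg has 70 × 80 / 30.97 = 181 at CrCl 38 and 5600 / 35.86 = 156 at CrCl 44. He is excluded at ULN 90 but not at ULN 110. The criterion catches some patients, not all.
- *Duplicate pre-treatment chemistry (section 7.2.2.6.3).* Its purpose is to set a baseline. It places no condition on the later value.
- *Day 1 chemistry (Table 7-1).* It is drawn, but nothing requires the result to be seen before dosing.
- *Weeks 2 and 4, and in France also Weeks 1 and 3.* These come after the first dose.

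**3. How often could it happen?** The documents give neither the distribution of clearance nor its within-patient variation, so this is an illustration only. Assume independent normal variation with a within-patient CV of 5% to 10% and a limit of 40. Let p = P(value low) = Φ((40 − true)/(CV × true)). Then:

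- first sample normal, last sample low: (1 − p)p
- of these, allocated to deferasirox under 2:1 randomisation: × 2/3
- excluded by one repeat that is also low: (1 − p)p²

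| True CrCl | p (CV 5% to 10%) | Low last | × 2/3 | Excluded by repeat |
|---|---|---|---|---|
| 38 | 0.854 to 0.701 | 0.125 to 0.210 | 0.083 to 0.140 | 0.107 to 0.147 |
| 40 | 0.500 | 0.250 | 0.167 | 0.125 |
| 42 | 0.170 to 0.317 | 0.141 to 0.216 | 0.094 to 0.144 | 0.024 to 0.069 |
| 44 | 0.035 to 0.182 | 0.033 to 0.149 | 0.022 to 0.099 | 0.001 to 0.027 |

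The low-last share falls to 0.005 to 0.087 at a true clearance of 46 and to at most 0.022 at 50. These are shares of patients at the stated clearance, not of the trial population.

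**4. Effect on the primary estimate.** With 100 deferasirox patients and a response rate of 0.60 to 0.90, one patient turned from expected responder to non-responder costs 0.60/100 to 0.90/100, that is 0.6 to 0.9 percentage points. The planned 95% half-widths in Table 10-3 over the same range are 9.6 to 5.9 points.

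**The case against.** The strongest reply is that entry and stopping rules may properly differ. A fall in clearance on deferasirox may be drug toxicity, whereas one low value before treatment may be noise. Every exclusion in the laboratory block of section 5.3 carries the two-sample condition, so it looks deliberate, and the laboratory analysis likewise calls clearance below 60 mL/min notable only at two consecutive measurements (Table 10-1). All of this stands, and it is why the two-sample rule should stay. It does not explain why a low last value goes unrepeated when one more sample would settle it.

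A reader might infer that sections 5.3 and 6.3.1 contradict each other, or that such a patient must stop on Day 1 because of the screening result. The documents do not support that: Table 6-2 governs patients on treatment, and a screening value does not trigger it.

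Three further limits stand:

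- Where a stricter local limit applies, a last value below 40 requires a first value above that limit, which is rare. With an assumed limit of 60, a CV of 10% and a true clearance of 50, it is Φ(−2) × Φ(−2) = 0.0228 × 0.0228 = 0.0005. The table above therefore describes only sites using 40.
- Some patients excluded by a repeat will truly be above 40.
- The IRT manual, the Central Laboratory Manual and the Investigator's Brochure are not available here and may contain an alert or hold.

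**Conclusion.** The point holds as a minor patient-safety improvement. On the protocol text, a patient whose first screening clearance is acceptable and whose last is low can be randomised and start deferasirox without a repeat, and no other written rule reliably prevents it. Early chemistry limits the length of exposure, and the investigator may stop treatment, but neither bars the first dose.

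The number affected cannot be estimated from the documents and is probably small. The percentages in the working depend on an assumed CV and on independence between samples, and they say nothing about how many enrolled patients lie near 40 mL/min. A reader might also infer a threat to the primary result. There is none of any size: each early stop costs less than one percentage point, well inside the planned interval.

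**What to change.** Keep the two-sample exclusion. Add to section 5.3, the protocol summary and the IRT eligibility check:

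*If the week -2 (most recent) creatinine clearance is ≤ 40 mL/min, or at or below the stricter local limit, one repeat sample must be resulted before randomisation and within the screening period. The patient is excluded if the repeat is also ≤ 40 mL/min or at or below that limit.*

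The ≤ boundary matches section 5.3, and allowing a single repeat prevents retesting until a value passes. Settling the matter before randomisation avoids holding a patient who already belongs to the Full Analysis Set. The repeat can be the scheduled Day 1 chemistry drawn early. If the central result cannot be awaited, section 7.2.2.6 already permits a local test with a paired central sample. Because that section bases eligibility on central results, the amendment should say that a local result is acceptable for this repeat.

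The cost is one protocol sentence and one IRT rule, an occasional extra blood test, a short delay and a few more screen failures near the limit, some in patients whose true clearance is above it. Patients who would have been allocated to phlebotomy face the same hold, although Table 6-2 sets no clearance stop for them. Where a stricter local limit applies, the hold also covers values between 40 and that limit. That part rests on the local contraindication that section 5.3 already adopts, not on Table 6-2. The SAP needs no change.
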